We hypothesize that the iLet BP will be non-inferior to the iPhone-based BP in dose administration and blood glucose control while subsequently improving user satisfaction with the device. We also hypothesize that Xeris glucagon in the iLet BP will be non-inferior to Lilly glucagon in the iLet BP in both infusion site reactions and occlusions.

In the Infusion Set Sub-Study, we hypothesize that the iLet infusion set will be non-inferior to the Contact Detach infusion set in plasma insulin levels, blood glucose control, and user experience.

The specific aims of this study are:

Aim 1. To conduct an outpatient study testing the safety and efficacy of the iLet BP versus our iPhone-based BP in up to 10 adult (≥ 18 years of age) subjects with type 1 diabetes in the fasted state, after a meal, and during and after exercise.

The study for this Aim will consist of two 8-hour study arms in random order: one with the iPhone-based BP and one with the iLet BP. Subjects will arrive fasting and remain fasted until the lunch meal. They will exercise on a stationary bike bpm for approximately 30 minutes with a heart rate from 120–140, starting at least 2 hours after lunch. The primary outcome will be the average percent dose amounts of both insulin and glucagon calculated by the control algorithm that are successfully delivered by the pump. Important secondary outcomes will include other metrics of device function (plasma insulin and glucagon levels will be measured every 30 minutes throughout the experiment) and measures of glycemic regulation, including mean CGM glucose and hypoglycemia exposure (% time <60 mg/dl).

Aim 2. To conduct an outpatient study testing the safety and efficacy of the iLet BP with Lilly glucagon versus Xeris glucagon in up to 10 adult (≥ 18 years of age) subjects with type 1 diabetes

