Volunteers who fit the selection criteria will be considered as candidates for this study. We will contact individuals who have previously inquired about participation in our studies and have asked us to have their contact information kept on file. In addition, advertisements for the study may be posted at the MGH Diabetes Center and other places, and may be distributed in the weekly broadcast email of research studies seeking volunteers. A letter may be sent to adult endocrinologists in the Boston metropolitan as well as selected nearby endocrinologists informing them of the study and asking them to refer any eligible patients who might be interested. We will post information about the trial along with contact information on our website

www.bionicpancreas.org and on www.clinicaltrials.gov.

IV. Subject Enrollment

IV. a. Number of Subjects

It is expected that we will have up to 10 subjects complete the study with a consistent protocol. We expect that the experiments can be accomplished over a period of 6 months. Up to 20 subjects with type 1 diabetes will be enrolled. The upper bound is based on the expectation that some volunteers will be excluded after the screening visit and the possibility that some experiments may have to be discontinued before completion (due to, for instance, intercurrent illness or subject withdrawal).

It is expected that we will have up to 10 subjects complete the Infusion Set Sub-Study with a consistent protocol. We expect that the experiments can be accomplished over a period of 6 months. Up to 20 subjects with type 1 diabetes will be enrolled. The upper bound is based on the expectation that some volunteers will be excluded after the screening visit and the possibility that some experiments may have to be discontinued before completion (due to, for instance, intercurrent illness or subject withdrawal).

The total enrollment for the study, including the infusion set sub study will be up to 40 subjects.

IV. b. Enrollment Procedures

Prospective participants will be briefed by a study staff member by phone or secured e-mail (using the "Send Secure" encryption) regarding the study procedure and the inclusion and exclusion criteria. Potential subjects will be sent an informed consent document by mail, fax, or secured e-mail. Subjects will be discouraged from discussing medical issues by non-secure e-mail, according to institutional policy.

IV. c. Consent Procedures

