- Medical, surgical and social history, allergies and review of systems relevant to inclusion and exclusion criteria
- Medications (prescription and non prescription)
- Type of insulin used in pump
- Average total daily dose in the last 30 days (from pump history)
- Height and weight
- Blood pressure
- Urine HCG (pre-menopausal females)
- Hemoglobin
- Hemoglobin a1c

During Study Visits:

- Insulin analog given
- Basal rates for the duration of the experiment, and carbohydrate ratio and correction factor used for the meal bolus
- Timing and content of the meal eaten, including carbohydrate count
- Timing and amount of insulin dose given for the meal
- Plasma glucose levels at least every 30 minutes, more frequently in the low range
- Plasma insulin levels every 20-30 minutes (assayed with Mercodia Iso-insulin ELISA)
- Total insulin given throughout the experiment
- Timing and amount of any carbohydrates taken for hypoglycemia
- Infusion site assessments including pain, skin reactions, appearance of site, and any evidence of leaks
- Timing of any infusion site replacements
- Subject reports of symptoms of any other complaints
- User satisfaction with both infusion sets

VI. b. Study Endpoints

VI. b. 1. Primary endpoint analyses

Aim 1: This will be generated from the bionic pancreas data during each arm:

- Average percent dose amounts calculated by the bionic pancreas control algorithm that are successfully delivered by the pump (aggregate of both insulin and glucagon doses).

Aim 2:

This will be generated from the bionic pancreas data during each arm:

- Average percent dose amounts calculated by the bionic pancreas control algorithm that are successfully delivered by the pump (glucagon doses).

Aim 4: Insulin Area Under the Curve in the 3.5 hours following the insulin bolus

VI. b. 2. Secondary endpoint analysis – Infusion Set Sub-Study

- During the initial 90 minute fasted period:
 - AUC
 - Mean insulin levels
 - Difference between insulin levels at baseline and at 90 minutes
- After the insulin dose:
 - T_{max}
 - T_{½max}
 - C_{max}
 - AUC in the first 30 minutes
 - AUC in the first 60 minutes
 - AUC in the first 90 minutes
 - Terminal half-life
- Difference between the fasted PG value and the PG value at 90 minutes
- Difference in PG prior to the meal and peak post-prandial glucose
- PG AUC in the 3.5 hours following the meal
- Number of infusion sites replaced for clinically suspected failure
- Local skin reactions
- Infusion site pain

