The primary analysis of the designated endpoints will be calculated on an intention-to-treat basis. In cases where an arm was not completed (and that arm was not repeated according to protocol criteria) we will use the available data from that arm in the data analysis. We will only include arms that were started by the subject.

We will use the Shapiro-Wilk test to determine the normality of the residuals for each comparison and calculate percentages, means or medians, and standard deviation and/or ranges as appropriate in descriptive analyses. We will use paired t-test or the Wilcoxon signed rank test for comparison of means with normally or non-normally distributed residuals, respectively. In a secondary analysis we will look for any period effect and any interaction between treatment and period, although no such interaction is predicted for the primary outcome, and there is probably insufficient power to identify a small interaction.

VI. c. Power Analysis

The power analysis is based on data from previous studies using the iPhone-based BP. The following table shows the percentage of time that the insulin and glucagon pumps were available to deliver doses calculated by the bionic pancreas. When pumps were not available, this was typically due to loss of communication between the iPhone and the t:slim pumps, but could also be due to pump occlusion or inadequate drug in the reservoir, among many other possible reasons.

Table 1. Time that pumps were available in previous bionic pancreas studies

| Study | insulin | | Glucagon | |
|------------------------------|---------|-----|----------|-----|
| | Mean | SD | Mean | SD |
| Beacon Hill | 96.5 | 2.7 | 95.9 | 2.3 |
| Camp1 | 93 | 2.7 | 92.2 | 2.3 |
| Camp2 | 95.1 | 2.5 | 93.9 | 3.1 |
| Multi-center | 96.1 | 2.5 | 95.9 | 2.5 |
| Mean | 95.2 | 2.6 | 94.5 | 2.6 |
| Min | 93.0 | 2.5 | 92.2 | 2.3 |
| Max | 96.5 | 2.7 | 95.9 | 3.1 |
| ttest (insulin vs. glucagon) | | | 0.044 | |

The glucagon pump was unavailable a greater percentage of the time than the insulin pump in the iPhone-based BP. This could be due to more frequent reservoir changes (the glucagon reservoir had to be changed every day, while the insulin reservoir was changed every other day – the pumps were unavailable during the reservoir change process), greater number of occlusions in the glucagon tubing and infusion sets, or possibly other, unknown factors.

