We anticipate that the iLet BP will be much more reliable in terms of delivering calculated doses because it does not rely on wireless communication between the device running the control algorithm and the pumps. In the iLet, the control algorithm and pumps are integrated into a single device. Nonetheless, there may still be times that the pump is unavailable or that the full dose is not delivered (e.g. due to temporary loss of communication between components due to software issue, tubing occlusion, or inadequate drug in the reservoir). Therefore, we anticipate that the percentage of the dose amount calculated that are delivered will be substantially greater, but not 100%.

We have modeled the power to detect a difference between the iPhone-based and iLet BPs based on an aggregate rate of pump unavailability of the iPhone-based BP (including both the insulin and glucagon pumps) of $96\pm 2.5\%$, which is close to the maximum reliability that we observed in the more reliable insulin pump across the 4 previous studies. We then calculated the power based on different possible reliabilities of the iLet internal pumping systems, based on 2-fold, 5-fold, and 10-fold reductions in pump unavailability, corresponding to availabilities of $98\pm 2.5\%$, $99.2\pm 2.5\%$, and $99.6\pm 2.5\%$, respectively. Under these assumptions, the sample sizes required for each of these possible outcomes to achieve a power of 80% with an alpha of 5% using a 2-sided test are 25 subjects, 10 subjects, and 8 subjects respectively. We expect a reduction of at least 5-fold in pump unavailability (and 10-fold would not be surprising), so 10 subjects should provide sufficient power to detect a difference. The standard deviations are assumed to be unchanged in these calculations, although it is likely that the standard deviations would also be reduced if the pump becomes more reliable - this means that the sample size estimates are likely conservative.

As the Infusion Set Sub-Study is a pilot study of the modified infusion set, no formal power calculations have been done for this portion of the study.

VI. d. Criteria for Success of the Study

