The main criteria for the success of the study will be that we observe a significant improvement in the primary outcome measure (and the related secondary reliability measures) in the iLet vs. the iPhone-based BPs, and no significant difference in the glycemic control measures. It is possible that improved reliability may actually improve glycemic control measures, but the sample size may not be sufficient to detect any such difference. A secondary criterion for success of the study will be that we observe no statistical difference in safety-related outcomes (occlusions, infusion site reactions or pain, nausea) between Xeris and Lilly glucagon.

The main criteria for the success of the infusion set sub-study will be that we observe no significant difference in the performance of the iLet infusion set when compared with the Contact Detach. Achieving a non-inferior result would allow us to move forward in future testing of the iLet infusion set with the iLet bionic pancreas in outpatient trials.

VII. Risks and Discomforts

Subjects may experience mild discomfort associated with the insertion of the infusion sets and sensor into the SC tissues. The risk of discomfort due to insertion of infusion sets and sensors is expected to be greater than in their lives outside the trial because more infusion sets will be inserted and a CGM sensor will be inserted, which may not be used in usual care.

There is a potential risk of hypoglycemia, since exogenous insulin will be administered. Due to frequent monitoring of glucose and direct supervision by an RN or MD at all times, the risk of a hypoglycemic episodes leading to significant harm to volunteers is expected to be substantially lower than their risk during their usual therapy.

There is a risk of hyperglycemia. This risk is expected to be less than the risk during the subjects' lives outside of the trial based on data from earlier trials.

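### The infusion-set sub-study counts a non-significant difference in at most 10 subjects as success and reads it as non-inferiority, with no margin or confidence-interval rule

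*Combined protocol and SAP*

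**What the plan says.** - **Hypothesis (II. Hypothesis and Specific Aims):** "we hypothesize that the iLet infusion set will be non-inferior to the Contact Detach infusion set in plasma insulin levels", and likewise in glucose control and user experience.
- **Success criterion (VI.d):** success means that "we observe no significant difference in the performance of the iLet infusion set when compared with the Contact Detach".
- **Consequence (VI.d, next sentence):** "Achieving a non-inferior result would allow us to move forward in future testing of the iLet infusion set".
- **Sample (IV.a):** "It is expected that we will have up to 10 subjects complete the Infusion Set Sub-Study". There is no minimum.
- **Test (analysis paragraph at the end of VI.b):** "We will use paired t-test or the Wilcoxon signed rank test for comparison of means", the choice depending on normality of the residuals.
- **Power (VI.c):** the sub-study is called a pilot, and "no formal power calculations have been done for this portion of the study".
- **Endpoints:** the Aim 4 primary endpoint in VI.b.1 is "Insulin Area Under the Curve in the 3.5 hours following the insulin bolus". VI.b.2 adds a long list of pharmacokinetic, glucose, skin, pain and satisfaction endpoints, including "Number of infusion sites replaced for clinically suspected failure". None has a pass rule.

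No section gives a non-inferiority margin, an equivalence range or a rule based on a confidence interval.

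**The concern.** The hypothesis is non-inferiority, but the only operational rule is failure to reject equality. A paired test that does not reach significance may mean that the sets perform alike, or that the study was too small or too noisy to tell. The rule cannot separate the two and rewards the second: fewer completers or a less precise assay make success more likely.

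The criterion also does not say which endpoint defines performance. Reading it as the AUC alone, or as every listed endpoint, gives different pass rates, and the choice could be made after the data are seen.

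The result matters because the sub-study is a gate. Section II presents it as required before human experiments with the iLet continue, and I.d says that earlier infusion-set flaws caused such experiments to be suspended. Passing a set that delivers too little insulin is the obvious hazard; VII.a says hyperglycemia risk may be raised by the investigational set. Excess exposure also matters, since VII.a lists hypoglycemia among the sub-study risks.

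**Working it through.** The plan gives no sample-size or power figure for the sub-study, so there is none to reproduce. The check asks how often the stated criterion would be met if the sets truly differed.

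**Inputs from the plan.** Two-period crossover, so paired data (II); n = 10 completers at most (IV.a); paired t-test (VI.b).

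**Assumptions.** Two-sided 5% level, which VI.c states for Aim 1 only. For the AUC figures: AUC alone decides, log AUC is analysed, and the within-subject CV is 10% to 40%.

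**Step 1, without a CV.** For a true shift of δ standard deviations of the paired differences, the t statistic is noncentral t with n−1 df and noncentrality δ√n. The pass probability is P(|T| < t(0.975, n−1)).

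| True shift | n = 10 | n = 8 | n = 6 |
|---|---|---|---|
| 0.5 SD | 71% | 77% | 83% |
| 1.0 SD | 20% | 32% | 49% |

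With n = 10, t(0.975, 9) = 2.262, so the 95% interval has half-width 2.262/√10 = 0.72 SD. Power of 80% is reached only for a true shift of about 1.0 SD.

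**Step 2, on the AUC ratio (iLet/Contact Detach), n = 10.** The SD of the paired log difference is s = √(2 ln(1 + CV²)), and δ = |ln(ratio)|/s. At CV 25%, s = √(2 ln 1.0625) = 0.348. For a ratio of 0.80, δ = 0.223/0.348 = 0.64 and the pass probability is 56%.

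| CV | 20% loss passes | 30% excess passes | Largest observed loss still non-significant | Lower 95% limit at that loss |
|---|---|---|---|---|
| 10% | 0.7% | 0.1% | 10% | 0.82 |
| 15% | 16% | 6% | 14% | 0.74 |
| 20% | 39% | 25% | 18% | 0.67 |
| 25% | 56% | 43% | 22% | 0.61 |
| 30% | 67% | 57% | 26% | 0.55 |
| 40% | 79% | 72% | 32% | 0.46 |

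The last two columns are 1 − exp(−2.262 s/√10) and exp(−2 × 2.262 s/√10), taking the sample SD equal to s. At CV 25%, an observed 22% loss, with an interval reaching down to a ratio of 0.61, would count as success. A simulation of 200,000 trials at CV 25% gave 56.0% and 43.4% for the two pass rates.

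**Step 3, if every endpoint must be non-significant.** The step 2 rates are then upper bounds. With five endpoints sharing the same standardised loss and pairwise correlation 0.8 (an invented scenario), the 20%-loss rates fall to about 0.1/4/18/33/45/60% at CV 10/15/20/25/30/40%.

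**Step 4, what a proper rule could deliver with n = 10.** Take an illustrative lower margin of 0.80, an illustrative upper bound of 1.25 and a true ratio of 1. Power on the lower limit is P(T > 2.262) with noncentrality (−ln 0.80/s)√10; the two-bound figures are simulated.

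| CV | Lower 95% limit above 0.80 | Both bounds, 95% CI | Both bounds, 90% CI |
|---|---|---|---|
| 15% | 85% | 69% | 85% |
| 20% | 61% | 29% | 51% |
| 25% | 44% | 10% | 24% |
| 30% | 33% | 3% | 10% |
| 40% | 21% | 0.4% | 2% |

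At CV 25%, the lower-limit rule alone passes a set with a true ratio of 1.3 in 97% of trials. With both bounds and the 95% interval, that falls below 1%, and a true ratio of 0.80 passes in at most 2.5%.

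**The case against.** The strongest reply is that this is a declared pilot. Success leads only to further trials, not to approval, and oversight by the monitoring board and FDA continues (IX.b). Sites are inspected after insertion, hourly and at the end (V.d.5), and replaced on suspicion of failure (V.d.7). These points are true, and the pilot label explains the missing power calculation. None of them supplies a decision rule or supports the word non-inferior.

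Second, the AUC figures depend on assumptions. This stands: the 20%-loss rate runs from 0.7% to 79% with the assumed CV alone, and large losses are usually caught at moderate CV (a 40% loss passes 0.1%, 1.6% and 6.8% of the time at CV 20%, 25% and 30%). The results in SD units need no CV, and the logical gap needs no figures.

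Third, the hypothesis is one-sided, both sets use the same cannula gauge and length (V.c.4), and the documents give no mechanism for excess exposure. The third part is fair, so the upper bound is a safeguard rather than a response to a demonstrated hazard. But the present criterion is already two-sided, and a lower-limit rule alone would remove that check.

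Fourth, the single Aim 4 primary endpoint is the natural reading of performance. That is reasonable, but VI.d does not say so.

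**Conclusion.** The concern holds, and VI.d is wrong as written: its criterion cannot support the non-inferiority conclusion that the next sentence draws from it. At the maximum planned sample, a deficit of 0.5 SD of the paired differences passes 71% of the time, assuming a paired t-test at two-sided 5%. On the AUC scale, the chance of passing a true 20% loss is negligible at CV 10% and above one half from CV 25%, provided AUC alone decides. Those AUC figures are illustrations, because the documents give no CV.

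The same reasoning applies to two other criteria in VI.d, for glycemic control and for Xeris versus Lilly safety outcomes. They also rest on absence of a significant difference and were not quantified here.

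**What to change.** In VI.d, name the 3.5-hour insulin AUC as the deciding endpoint for Aim 4. Analyse paired log AUC and report the iLet/Contact Detach geometric mean ratio with a two-sided confidence interval. Then take one of two routes.

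1. **Non-inferiority.** Claim it only if the lower limit exceeds a margin that the sponsor fixes and justifies before the data are seen. Also read the upper limit against a prespecified bound. The 0.80 and 1.25 used in the working are illustrations, not proposals.
2. **Descriptive pilot.** Report the ratio and interval, allow inconclusive as a result, and remove the non-inferiority wording from VI.d and from the sub-study hypothesis in section II.

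Under either route, state how site failures, skin reactions and pain enter the decision, or say that they are descriptive. For the glycemic and Xeris-versus-Lilly criteria, report paired differences with confidence intervals and state that non-significance does not show non-inferiority.

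The cost is rewording VI.d and one sentence of the analysis paragraph (plus the hypothesis under route 2), with no added subjects or visits. The downside is that many results will be inconclusive with 10 subjects: under the illustrative limits, power at CV 25% is 44% for the lower limit alone and 10% for both bounds with a 95% interval. From about that CV upward, the descriptive route is the realistic one for this sample.

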| ISO | International Organization for Standardization |
| MARD | Mean Absolute Relative Difference |
| MD | Doctor Of Medicine |
| MEN2A | Multiple Endocrine Neoplasia, type 2A |
| MEN2B | Multiple Endocrine Neoplasia, type 2B |
| MGH | Massachusetts General Hospital |
| MPC | Model-Predictive Control |
| NOAEL | No Observed Adverse Effect Level |
| PI | Principal Investigator |
| PK | Pharmacokinetics |
| RF | Radio Frequency |
| RN | Registered Nurse |
| SC | Subcutaneous |
| SGLT-2 | Selective sodium-glucose transporter-2 inhibitors |
| T1D | Type 1 Diabetes |
| UI | User interface |
| VAS | Visual Analog Scale |
| YSI | Yellow Spring Instrument |
